#### **9.4 Vital signs**

Summary tables of observed values and changes from baseline, as well as minimum and maximum post-baseline values, will be presented for vital-sign data, including weight (g), body temperature (°C), respiration rate (breaths/minute), pulse rate (bpm), systolic blood pressure (mmHg), diastolic blood pressure (mmHg), and pulse oximetry (%), at each visit on a given timepoint, in the Safety population.

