### 1.2.2 Nonclinical pharmacokinetics

In animal PK, toxicological, and infection model studies, IV ceftobiprole medocaril was rapidly hydrolyzed in plasma to the active moiety ceftobiprole by multiple enzymes, including plasma esterases, and also non-enzymatically. The volume of distribution of ceftobiprole was restricted to the extracellular compartment, and its elimination occurred predominantly by passive glomerular filtration of unchanged ceftobiprole. The beta-lactam open-ring was the main metabolic product.

In rats, excretion was almost complete within 4 days after IV administration of ceftobiprole medocaril. Penetration of ceftobiprole into lungs and brain in infected animals was demonstrated.

Based on cytochrome P450 inhibition data, the potential of ceftobiprole to exhibit clinically relevant drug-drug interactions is small. Protein binding of ceftobiprole in plasma of rats, rabbits, marmosets, cynomolgus monkeys, and dogs was low (approximately 10% to 45%) and concentration-independent. Plasma protein binding in humans was also low (approximately 16%) and concentration-independent.

Toxicokinetic monitoring during toxicity studies in rats, rabbits, marmosets, cynomolgus monkeys, and dogs demonstrated high and approximately dose-proportional exposures to

ceftobiprole in all species, exceeding the expected human therapeutic exposure at the no-observed-adverse-effect level (NOAEL). There were no relevant indications of accumulation, differences related to sex, or time-dependent PK.

In neonates and juveniles male and female rats administered daily from Day 1 post-partum until Day 49, which covers the human age range from neonates up to teenagers, dose-proportional exposure of the pups and decreased half-life and exposure to ceftobiprole with increasing age was demonstrated, as a consequence of increased renal clearance. There were no gender-differences. This study provides a safety margin of 2 to 6 for pediatric patients (neonates up to < 18 years) with the optimized dosing regimens.

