At the highest dose of 250 mg/kg/day (187.5 mg/kg/day ceftobiprole), effects on clinical condition and reduced body weight prior to weaning were seen. Differences in crown to rump and bone measurements were considered related to the lower body weight. Gross pathological and histopathological changes at the injection site were noted, and microscopic changes in the kidneys were seen at the end of treatment. Based on these findings, the NOAEL in juvenile rats was 100 mg/kg/day (75 mg/kg/day ceftobiprole).

In summary, the nonclinical toxicology profile of ceftobiprole is consistent with that seen with antibiotics of the beta-lactam class, and the observations in juvenile animals were similar to those seen in adult animals.

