Extrapolation of the model to pre-term neonates and young infants was deemed appropriate given the dependence of ceftobiprole PK on glomerular filtration rate and body weight, which are both well described in this population. Glomerular filtration rate was assigned using a standard equation that assumed normal renal function, adjusted for age and body surface area using fat-free mass ([Rhodin 2009](#)). Body weight and height were assigned using a set of polynomial longitudinal growth equations, which define body weight and height over time based on gender, gestational age, and post-natal age ([Troutman 2018](#)).

Model-based simulation analyses to assist in the ceftobiprole dose selection for the treatment of LOS in pre-term and term neonates and young infants assessed several dose regimens before identification of an optimal regimen ([Table 5](#)). The optimal dose regimen, with dose adjustment according to gestational and post-natal ages, was predicted to result in a consistent ceftobiprole exposure and adequate PK-PD target attainment similar to those in adults and older pediatric patients. In general, the median predicted AUC0-24 values fall within the mean  $\pm$  two standard deviations from the adult Phase 1 exposures from the multiple-ascending dose study. The 90% prediction intervals fall outside the range but remain acceptable. In contrast, ceftobiprole Cmax estimates were predicted to be lower than those observed in healthy adults, with the exception of the patients in the oldest gestational age group ( $\geq 37$  weeks), which are similar to adults.

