#### 5.5.2 Physical examination

A complete physical examination will be performed at Screening and at the EOT and TOC visits in accordance with [Table 3](#), and will include examination of general appearance, skin, head, neck, eyes, ears, nose, throat, cardiovascular system, thorax/lungs, abdomen, lymph nodes, extremities, and nervous system.

Complete or targeted physical examinations focusing on changes from baseline will be performed during the active treatment period at the discretion of the Investigator as clinically indicated in accordance with local standard of care.

Any clinically-significant physical change from baseline that occurs after first study-drug

administration must be reported as an AE (see Section [7.4](#)).

A patient's length will be measured only during the Screening visit.

Body weight will be measured at Screening, daily during the active treatment period, and at the EOT and TOC visits. The weight obtained within 12 hours prior to the first dose of study drug will be used to calculate the dose on Day 1. From Day 2 until the last day of study treatment, the dose should be calculated based on the patient's first body weight of the day.

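### Body weight is summarised only in raw grams, so slowed growth would normally be tabulated as a gain; a rate and a percent-of-expected measure should be added

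*SAP*

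**What the plan says.** SAP 9.4 plans tables of observed values, change from baseline and post-baseline extremes, which "will be presented for vital-sign data, including weight (g"), at each visit, in the Safety population. SAP section 4 presents summaries by term, pre-term and overall, and lists all data by patient. SAP 4.3.3 uses no visit windows, so the TOC row is the nominal visit whenever it took place.

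Protocol 5.5.2 sets the schedule: "Body weight will be measured at Screening, daily during the active treatment period, and at the EOT and TOC visits". No weight is scheduled at last follow-up. The same section says that "length will be measured only during the Screening visit", so weight is the only scheduled measure of growth after baseline. It also requires a clinically significant physical change after first dosing to be reported as an adverse event.

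On the animal data, protocol 1.2.3 reports that at the top dose in neonatal and juvenile rats (250 mg/kg/day) "effects on clinical condition and reduced body weight prior to weaning were seen", and that "the NOAEL in juvenile rats was 100 mg/kg/day". Protocol 1.2.2 adds: "This study provides a safety margin of 2 to 6 for pediatric patients".

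For dose simulation, protocol 1.4.3 already relies on growth equations "which define body weight and height over time based on gender, gestational age, and post-natal age".

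**The concern.** Raw change from baseline suits pulse or temperature, where no change is the neutral result. Weight in a neonate should rise, so a positive change is what both normal and slowed growth produce. The planned extremes help little: in a growing infant the minimum is probably an early weight near baseline and the maximum is the latest weight. SAP 9.3 flags laboratory values against normal ranges, but weight gets no reference of any kind.

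Two features of the design make the grams harder to read. The baseline-to-TOC interval depends on course length and visit timing. The pre-term group also mixes infants of very different size: protocol 8.4 foresees summaries by gestational and post-natal ages as appropriate, whereas the SAP splits only term from pre-term.

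At stake is one component of the primary safety endpoint, which covers vital signs and physical examination findings. A reader who sees a positive mean change may take it as no effect on growth when the table could not have shown slowed growth.

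**Working it through.** The documents state no growth figure, so there is nothing of the plan's own to reproduce.

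**Inputs from the documents**
- Treatment lasts 3–10 days, up to 14; TOC is 7–14 days after the last dose (protocol section 3).
- First dose to TOC: 3 + 7 = 10 days to 14 + 14 = 28 days, approximately.
- Planned sample: 2 term + 6 pre-term = 8.

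**Assumptions (not in the documents)**
- Expected velocity v: 15 g/kg/day, range 10–20.
- Baseline weight W0: 1,500 g for illustration; 700–3,000 g in the simulation.
- Between-infant SD of velocity: 3 or 5 g/kg/day.

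**Step 1: what the change column shows.** Expected change = W0 × (exp(v·d/1000) − 1); at half rate, W0 × (exp(v·d/2000) − 1). For W0 = 1,500 g and v = 15:

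| Days d | Expected | Half rate | Deficit | Deficit as % of expected weight |
|---|---|---|---|---|
| 3 | +69 g | +34 g | 35 g | 2.2% |
| 10 | +243 g | +117 g | 126 g | 7.2% |
| 14 | +351 g | +166 g | 184 g | 10.0% |
| 28 | +783 g | +351 g | 432 g | 18.9% |

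Over v = 10–20 the percentage deficit is 1.5–3.0% at 3 days, 4.9–9.5% at 10 days, and 13.1–24.4% at 28 days. It does not depend on W0.

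**Step 2: effect of the interval.** Normal growth alone gives 783/243 = 3.2 times as many grams at 28 days as at 10. The table also shows +351 g twice: for normal growth over 14 days and for half-rate growth over 28 days. This equality holds for any v, because v × 14 = (v/2) × 28, and both intervals are allowed. Grams cannot separate these two infants. Velocity can: 1000 × ln(1,851/1,500)/14 = 15 g/kg/day against 1000 × ln(1,851/1,500)/28 = 7.5 g/kg/day.

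**Step 3: a pre-term group of six.** Simulated with W0 uniform on 700–3,000 g, d uniform on 10–28 days, v normal, and 100,000 groups per setting:
- Half-rate infants with a positive raw change: 84–100%.
- Half-rate group means that are positive: at least 99%.
- Standardised gap between full and half rate: 0.66–1.02 SD in raw grams, 1.00–3.33 SD as velocity.
- Chance that a half-rate group mean falls below the 5th percentile of full-rate means: 0.62–0.96 in raw grams, 0.79–1.00 as velocity.

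The last comparison needs the full-rate distribution as a yardstick, and the SAP supplies none.

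**The case against.** A reader might infer that a growth signal cannot appear at all. The documents do not support that. Actual weight loss would show in the change and minimum values. Serial weights are listed by patient, which is workable with eight infants, and a clinically significant physical change must be reported as an adverse event. These routes stand, but none applies a growth criterion, and the listings give no expected value.

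A reader might also infer that differences in infant size alone would swamp a halving of growth. The term/pre-term split already removes much of that contrast, and in the model above gain is proportional to starting weight, so a size comparison only restates the weights chosen. Spread within the pre-term group and the varying interval remain.

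The animal link is limited too. The rat effect arose above the NOAEL, with daily dosing from Day 1 to Day 49 post-partum, against 3–14 days of treatment here. The stated use of the daily weights is dose calculation, and growth is not an adverse event of special interest. The finding is a reason to display weight usefully, not evidence of harm in infants.

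Finally, sepsis, feeding intolerance and fluid shifts all affect weight, and there is no control arm. No summary measure can remove that limit.

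**Conclusion.** The point holds as a weakness of presentation in a descriptive safety output. Every planned weight summary is in unstandardised grams, over an interval that varies almost threefold (28/10 = 2.8) to TOC. Growth at half the expected rate would normally be tabulated as a gain, while the infant ends about 5–10% below expected weight at 10 days and 13–24% below at 28 days under assumed rates of 10–20 g/kg/day. That half of a positive rate is still a gain, and that 14 normal days equal 28 half-rate days in grams, does not depend on the assumed rate. The percentages and simulation results do.

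The documents do not support saying that the signal is hidden altogether, that the drug slows growth in patients, or that a standardised measure would settle causation. After a 3-day course the shortfall is only 1.5–3.0%, so EOT would show little on any scale.

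**What to change.** Keep the raw-gram summary in SAP 9.4, because it is the table that shows weight loss, and add two derived variables:

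1. Weight velocity in g/kg/day from baseline to EOT and from baseline to TOC, using actual dates: 1000 × ln(weight/baseline weight)/days.
2. Weight at TOC as a percent of that expected for sex, gestational age and post-natal age, from one named reference, with the baseline percent beside it so that an infant already small at entry is not read as growing slowly. The growth equations cited in protocol 1.4.3 are a candidate. Change in z-score could replace it only if the chosen reference supplies dispersion; the protocol says only that those equations define weight over time.

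Present both by term, pre-term and overall. Make TOC the main time point, since EOT after a short course shows little and partly reflects fluid shifts. State in the SAP that the measures are descriptive and do not attribute slow growth to the drug.

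The cost is some SAP text, two derived variables and the choice of one reference. Sex, both ages, weights and dates are already collected, so no new data, visit or clinical procedure is needed.

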### **10 PHARMACOKINETICS**

Plasma concentrations of ceftobiprole, ceftobiprole medocaril, and the open-ring metabolite will be reported at each time point specified in the protocol Schedule of Assessments.

Non-compartmental PK analysis and a population PK model will be developed and reported separately.

### **11 INTERIM ANALYSES**

No interim analyses will be performed.

### **12 CHANGES IN THE PLANNED ANALYSIS**

There are no changes between the protocol-defined statistical analyses and those presented in this SAP.

The definition of the CE population has been clarified in this SAP. Patients should have received at least 48 hours of study drug to be included in the CE.

## 13 APPENDICES

### Appendix 1 Adverse event and prior/concomitant medication date imputations

#### Imputation rules for partial dates

##### *Adverse event start date imputation*

| Parameter          | Missing | Additional conditions                                   | Imputation                       |
|--------------------|---------|---|----------------------------------|
| Start date for AEs | D       | M and Y same as M and Y of first dose of study drug     | Date of first dose of study drug |
|                    |         | M and/or Y not same as date of first dose of study drug | First day of month               |
| D and M            |         | Y same as Y of first dose of study drug                 | Date of first dose of study drug |
|                    |         | Y is after Y of first dose                              | 1 January                        |
| D, M, Y            |         | None – date completely missing                          | Date of first dose of study drug |

D = day; M = month; Y = year; AE = adverse event.

Note: In all cases, if an estimated start date is after a complete stop date, use the first day of the stop date month.

##### *Prior and concomitant medication start date imputation*

| Parameter                 | Missing | Imputation                                 |
|---------------------------|---------|--|
| Start date for medication | D       | First day of the month under consideration |
|                           | D and M | 1 January                                  |
|                           | D, M, Y | 1 January of the year of informed consent  |
| Stop date for medication  | D       | Last day of the month under consideration  |
|                           | D and M | 31 December                                |
|                           | D, M, Y | 31 December of the year of follow-up visit |

D = day; M = month; Y = year.

Note: In all cases, if an estimated start date is after a complete stop date, use the first day of the stop date month.
